7.7.3 Visit Windows

The study protocol gives the overall study schedule and the permissible intervals for these visits expressed as the number of days relative to Visit 2.

Analyses will not exclude subject data due to the subject's failure to comply with the visit schedule.

All the assessments will be allocated to CRF visit based on the table below:

CRF visit	Target day	Planned assessment day	Analyzed visit
Visit 1	D-21	D-28 to D-3	Screening
Visit 2	D1	D1	Baseline
Visit 3	D7	D4 to D11	Day 7
Visit 4	D30	D16 to D46	Day 30
Visit 5	D180	D150 to D210	Day 180

The value with the assessment day that is the closest to the defined target day within the windows is used. If two values are equally close, one before and one after the target date, the value with the later date is used in the analysis.

7.7.4 Imputation Rules for Incomplete Dates

In case of missing partial start and stop dates for concomitant medications, the following rules will be used:

If the start date is missing or partial:

- if the month is missing, use January
- if the day is missing, use the first day of the month under consideration
- if the year is missing, use year of the informed consent date
- if the entire date is missing, use informed consent date

If the stop date is missing or partial:

- if the month is missing, use December
- if the day is missing, use the last day of the month under consideration
- if the year or the entire date is missing, set the stop date to December 31st, of the current year.

If the imputed start date is after the stop date, then the imputed start date will be 1 day prior to the stop date.

For AEs, a missing or incomplete onset date will be imputed according to the following conventions.

If an onset date is missing or only the year is known, the imputed onset date will be the date of first dose of study drug.

If only the year is known for the AE onset date, the imputed onset date will be the latest of the following non-missing dates:

- Date of first dose of study drug
- January 1 of the year of AE onset date

If only the month and year is known for the onset date, set the imputed onset date to the first day of that month and then apply the following rules.

- If the month and year of the onset date is prior to the month and year of the first dose of study drug, then the imputed onset date will be the imputed onset date.
- If the month and year of the onset date is on or after the month and year of the first dose of study drug, then the imputed onset date will be the latest of the following non-missing dates:
 - Date of first dose of study drug
 - Surrogate onset date

If the imputed onset date is after the adverse event end date, the imputed onset date will be the same as the adverse event end date.

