7.10 Handling of Missing Data, Outliers, Visit Windows and Other Information

As a general principle, no imputation of missing data will be done. Exceptions are the start and stop dates of AEs and concomitant medications if they are missing on day of first dose. The imputed dates will be used to assess if the AEs or concomitant medications are treatment-emergent or concomitant, respectively. Listings of the AEs and concomitant medications will present the actual partial dates; imputed dates will not be shown.

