6.2.1.1 Adverse Events

AE collection begins after the ICF has been signed and continues until screen failure, or for those enrolled, 30 days after study vaccine administration. A TEAE is defined as an AE observed after study immunization and up to 30 days post immunization. Medically attended adverse events (MAAEs) are AEs for which the subject has received medical attention by medical personnel, or in an emergency room, or which led to hospitalization. A new-onset chronic disease (NOCD), is defined as a MAAE which a) was absent at baseline; b) has not resolved at the follow-up telephone call; c) requires continuous medical care or attention.

PIMMCs are defined as any AEs of autoimmune or auto inflammatory nature. SAEs, MAAEs, which include PIMMCs and NOCDs, will be collected throughout the study, from vaccine administration on Day 1 up to the last follow-up visit (day 30 for Group 3; day 180 for Groups 1 and 2).

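### SAP 7.7.4 gives two rules for year-only AE onsets; they conflict only when the onset year follows the dose year, and the first rule can then label as a TEAE an event that cannot be one

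*SAP*

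**What the plan says.** SAP 7.7.4 lists the conventions for incomplete AE onset dates one after another.

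- First rule: "If an onset date is missing or only the year is known, the imputed onset date will be the date of first dose".
- Second rule: "If only the year is known for the AE onset date, the imputed onset date will be the latest of the following" two dates, namely the date of first dose and "January 1 of the year of AE onset date".
- Month-and-year rule: an onset in a month before the dose month keeps its pre-dose date. Otherwise the onset is moved no earlier than the dose date.
- End-date cap, which resets a late imputed onset to the day on which the event ended: "If the imputed onset date is after the adverse event end date, the imputed onset date will be the same as the adverse event end".

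No order of precedence is stated between the first two rules, and the revision history in SAP section 8 does not mention them.

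These dates decide how events are classified. Protocol 7.10 states: "The imputed dates will be used to assess if the AEs or concomitant medications are treatment-emergent or concomitant, respectively". SAP 6.2.1.1 sets the window: "A TEAE is defined as an AE observed after study immunization and up to 30 days post immunization". The same section says that "AE collection begins after the ICF has been signed", and that SAEs and MAAEs (including PIMMCs and NOCDs) are followed to day 180 in Groups 1 and 2 and to day 30 in Group 3. The protocol synopsis plans Stage 2 for 3Q2019 to 3Q2020, which crosses a year end.

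**The concern.** A year-only onset meets the condition of both rules. Where they disagree, two programmers could follow the SAP faithfully and produce different TEAE tables.

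TEAEs are a primary endpoint in both stages. SAP 7.5.1 tabulates serious, medically attended, immune-mediated and new-onset chronic events as TEAEs. Counts in such tables are likely to be low, so a single record can change a cell. Under SAP 7.6 the sponsor is unblinded after the day 30 data cut-off, while follow-up to day 180 continues. The choice between the rules should therefore be in writing beforehand.

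**Working it through.** The plan states no figure on this point, so the check is of date logic. Individual dose dates below are illustrations within the planned Stage 2 period.

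**Definitions.** D is the dose date and Y the known onset year.

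- First rule: onset = D.
- Second rule: onset = the later of D and 1 January of Y.
- Cap: if the AE end date is earlier than the imputed onset, onset = end date.
- TEAE: imputed onset 0 to 30 days after D. Counting day 0 is an assumption, because the definition does not address an onset imputed to the day of dosing.

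**Cases.**

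| D | Y | First rule | Second rule |
|---|---|---|---|
| 15 Oct 2019 | 2019 | 15 Oct 2019, TEAE | 15 Oct 2019, TEAE |
| 15 Oct 2019 | 2020 | 15 Oct 2019, TEAE, outside Y | 1 Jan 2020, day +78, not TEAE |
| 1 Dec 2019 | 2020 | 1 Dec 2019, TEAE, outside Y | 1 Jan 2020, day +31, not TEAE |
| 2 Dec 2019 | 2020 | 2 Dec 2019, TEAE, outside Y | 1 Jan 2020, day +30, TEAE |
| 10 Jan 2020 | 2019 | 10 Jan 2020, TEAE, outside Y | 10 Jan 2020, TEAE, outside Y |
| 10 Jan 2020 | 2019, AE ended 28 Dec 2019 | 28 Dec 2019, not TEAE (cap) | 28 Dec 2019, not TEAE (cap) |

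The 78 days are 16 left in October + 30 + 31 + 1.

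**Same year (Y = dose year).** Both rules give D, so there is no conflict.

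**Later year.** The rules always give different dates. TEAE status differs when 1 January is more than 30 days after D, so the last such dose date is 1 December 2019 (31 days). The first dose date for which follow-up of 180 days reaches 2020 is 5 July 2019 (5 July + 180 days = 1 January 2020). That is 27 + 31 + 30 + 31 + 30 + 1 = 150 dose dates. For each of them, any 2020 onset is more than 30 days after dosing, so the first rule labels as a TEAE an event that cannot be one. The cap does not help, because an event starting in 2020 cannot end before a 2019 dose. For doses on 2 to 31 December 2019 both rules give a TEAE, with different dates.

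**Earlier year.** Both rules give D, although the event was certainly before dosing. With Stage 2 screening of up to 40 days, this is possible for doses from 1 January to 9 February 2020 (9 February − 40 days = 31 December). Only a recorded end date before dosing corrects it, through the cap.

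**Who is left where TEAE status differs.**

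- Group 3 follow-up ends at day 30, so any next-year onset within it is inside the window under either rule.
- Stage 1 was planned for 1Q to 2Q2019. A dose on 30 June 2019 reaches 180 days on 27 December 2019, so later-year onsets are nearly excluded.
- Subjects dosed in 2020 have no 2021 follow-up if Stage 2 ends in 3Q2020 as planned.
- General AE collection stops at day 30, so only SAEs and MAAEs remain.

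The residue is essentially Group 2 subjects dosed in 2019 before about 2 December.

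**The case against.** The strongest reply is that this is a drafting slip of little consequence. The second rule deals with year-only dates specifically, and a programmer would plausibly let it govern. Year-only onsets should be rare in a single-dose study with prospective follow-up. SAEs must be reported within 24 hours of awareness (Protocol 5.5.5), incomplete entries can be queried (Protocol 8.1), and the data are reviewed before lock (SAP section 1). Protocol 7.10 keeps the actual partial date in the listings. The first rule also errs towards counting an event as treatment-emergent.

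Most of this stands and limits the size of the point. It does not settle which rule applies, and leaning towards over-counting does not justify a date that the recorded year rules out.

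A reader might infer more than the documents support:

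- **That the rules classify all year-only events in opposite ways.** They agree when the onset year is the dose year or earlier, and both give a TEAE for doses on 2 to 31 December.
- **That only the first rule moves an event out of its known year.** The second does the same for a prior-year onset.
- **That events recalled at the day 180 contact are known to have partial dates most often.** This is plausible, but neither document gives a rate.
- **That the comparison with PCV13 is biased.** The rules apply alike to both vaccines and the sites stay blinded until database lock (SAP 7.6), so no differential effect is shown.

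**Conclusion.** The contradiction is real, and its scope is narrow. SAP 7.7.4 contains two incompatible rules for year-only onsets. For a later-year onset after a dose more than 30 days before 1 January, the first rule gives a date outside the known year and a TEAE label that the 30-day definition excludes.

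The number of affected records cannot be computed from the documents, but it is expected to be small. The conclusion rests on these assumptions:

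- The 30-day TEAE definition in SAP 6.2.1.1 and Protocol 7.5.1 governs. Protocol 5.4.1 describes TEAEs and MAAEs together as assessed to the last follow-up visit. On that reading the October example would be a TEAE under both rules.
- An onset imputed to the day of dosing counts as a TEAE.
- Some Group 2 dosing took place in 2019 before about 2 December. The planned period allows this, and the amendment of 02 Dec 2019, which drops sentinels from Cohort 5 onward after review of previous cohorts, suggests but does not prove it.

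This is a minor correction, worth making because it bears on a primary endpoint.

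**What to change.** Make two edits in SAP 7.7.4.

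1. Remove the year-only alternative from the first AE rule, so that it covers only wholly missing onset dates and year-only dates follow the second rule. The October 2019 example then becomes 1 January 2020, not a TEAE.
2. Add a clause to the second rule: if the known onset year is before the dose year, the event is treated as pre-dose. The month-and-year rule already does this for earlier months. Without the clause, a 2019 onset with a dose on 10 January 2020 would still become a TEAE unless a pre-dose end date was recorded. The first edit alone is therefore only a partial repair.

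It would also help to state whether an onset imputed to the day of dosing counts as a TEAE. The cost is one deleted phrase, one added clause and the matching change to the derivation program. Data collection does not change.

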8 REVISION AND RATIONALE

Version 1 of the SAP has been updated to include planned interim analyses, provide greater details of treatment assignment blinding for study personnel, update the analysis of exploratory endpoints and to correct assorted typographical errors.

Version 2 of the SAP has been updated to

1. Increased screening for Stage 2 to be consistent with the protocol from -28 days to -40 days.
2. Added: “Subjects who are given PPSV23 without previous exposure to PCV13 will not be included in the immunogenicity summaries.” These are subjects in Stage 2, Group 3 who should have received PCV13 before receiving PPSV23.
3. **CCI** [REDACTED]
4. Changed the algorithm for setting the value for LLOQ for the calculation of fold change in response to feedback from the FDA. Values below the LLOQ will be set to $\frac{1}{2}$ LLOQ for calculation of geometric means and set to LLOQ for calculation of fold changes.
5. **CCI** [REDACTED]
6. **CCI** [REDACTED]
7. Added a CMH rank test to examine the difference between ASP3772 and PCV13 in the number of reactogenicity reactions. Added a CMH statistics with scores=modridit to compare the severity for each type of reaction between each dose of ASP3772 and PCV13 after assigning an increasing score to each severity.
8. Added details for determining systemic reactogenicity events during the 1st hour post vaccination.

10 APPENDICES

10.1 Appendix A: Instructions to calculate the Summary statistics for the secondary endpoints

Geometric Mean (GM) and Geometric Standard Deviation (GSD)

To obtain the GM and GSD, first calculate the natural log of each titer or IgG concentration using the LOG function in SAS. Using PROC FREQ on the log transformed values obtain the mean and standard deviation of the log transformed values. Exponentiate mean and standard deviation to obtain the geometric mean and geometric standard deviation.

To obtain the lower confidence limit of the 95% confidence interval of the GM obtain the critical value of the student's distribution using TINV(0.975, n-1) where n=the number of non-zero titers or concentrations. For example, TINV(0.975, 19) = 2.093. The lower 95% confidence interval is then:

$$GM / GSD^{(TINV(0.975, n-1) / SQRT(n))}$$

and the upper 95% confidence is calculated using: $GM \times GSD^{(TINV(0.975, n-1) / SQRT(n))}$

where SQRT is the square root.

Geometric Mean Ratio (GMR)

To obtain the geometric ratio, calculate the GM for each treatment group. The geometric mean ratio can then be calculated as;

$$GM_{ASP3772} / GM_{PCV13}$$

Alternately, calculate the natural log of each titer or IgG concentration using the LOG function in SAS to transform the titers or IgG concentrations. Obtain the mean of the log transformed values for each treatment group, μ_1 and μ_0 . To calculate the geometric mean ratio:

$$GMR = e^{(\frac{\mu_1 - \mu_0}{2})}$$

where μ_1 is the arithmetic mean of the log transformed ASP3772 titers (or concentrations) and μ_0 is the arithmetic mean of the log transformed PCV13 titers (or concentrations).

To test that the null hypothesis that the GMR = 1, use the two sample t-test for the treatment difference of the log transformed titers (or concentrations). This is equivalent to testing if the GMR is equal to 1.

To obtain the 95% CI for the geometric mean ratio:

- (1) Obtain the standard error of the difference for the log transformed values SE_{DIFF} .
- (2) Calculate the lower CI:

$$e^{\frac{GMR - (TINV(0.975, n(1)+n(2)-2)) * SE_{DIFF}}{n(1)+n(2)-2}}$$

- (3) Calculate the upper CI:

$$e^{\frac{GMR + (TINV(0.975, n(1)+n(2)-2)) * SE_{DIFF}}{n(1)+n(2)-2}}$$

Geometric Mean Fold Increase (GMFR)

To obtain the GMFR, calculate the fold rise for each subject. Take the natural log using LOG function in SAS. Using PROC FREQ on the log transformed values obtain the mean and standard deviation of the log transformed values. Exponentiate mean and standard deviation to obtain the geometric mean and geometric standard deviation.

To obtain the lower confidence limit of the 95% confidence interval of the GMFR obtain the critical value of the student's distribution using TINV (0.975, n-1) where n=the number of subjects. For example, with 20 subjects TINV (0.975, 19) = 2.093. The lower 95% confidence interval is then:

$$GM / GSD^{(TINV(0.975, n-1) / SQRT(n))}$$

and the upper 95% confidence is calculated using: $GM \times GSD^{(TINV(0.975, n-1) / SQRT(n))}$

where SQRT is the square root.

Comparing the Geometric Mean Fold Rise (GMFR) between two groups

To compare the GMFR between the two treatment groups (each dose of ASP3772 vs. PCV13) use an analysis of covariance with the log-transformed post immunization value as the dependent variable and the log-transformed pre vaccination value as the independent value. With log-transformed antibody values (titer or IgG levels) the variability usually decreases with increasing antibody values (heteroscedasticity).

Assume heteroscedasticity exists and use the following model to analyze the data.

```
proc mixed;  
  model y=group x group*x/ solution; repeated / local=exp ( x x2);  
  run;
```

Where: y= log-transformed post immunization antibody titer (or IgG concentration)

x= log-transformed pre immunization antibody titer (or IgG concentration)

x2=(log-transformed pre immunization antibody titer (or IgG concentration))² group= treatment group

group*x= treatment group by pre immunization log-transformed antibody titer (or IgG concentration). If group*x is significant then there is heteroscedasticity.

Use the ESTIMATE and CL options in proc mixed to obtain the estimate of the baseline corrected mean fold ratio and the 95% confidence interval for the baseline corrected mean fold ratio. The ratio is the GMFI for ASP3772 / PCV13. The baseline-corrected geometric mean ratio of the two treatment groups is:

2^{β_1} where β_1 is the estimate of the treatment group effect obtained from the ANCOVA. The 95% lower confidence limit is then $2^{\beta(LCL)}$ and the 95% upper confidence interval is then $2^{\beta(UCL)}$ LCL and UCL are the 95% confidence limits obtained from the CL option in Proc Mixed.

Proportion of subjects with a > 4-fold increase in OPA titer

SAS PROC FREQ can be used to obtain the proportions and 95 % CI for each serotype.
PROC FREQ data=xxxx order=freq;

```
tables fourfold / binomial (wilson) alpha=0.05;  
weight count;
```

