2, 5 μ g or PCV13) as the factor of interest will be conducted on the natural logarithm (log) of pneumococcal OPA titers and the natural log of the IgG concentrations.

In addition, for both Stage 1 Group 1 and Stage 2 Group 2, SP1500+0785 levels (ng/mL) will be collected for those subjects given either ASP3772 or PCV13. Levels of the following cytokines will be collected for subjects given ASP3772 or PCV13: Th17, IL-17, IL-17, IL-22, The units for all are pg/mL. Non-parametric methods will be used for these analyses. A Kruskal-Wallis test will be used to test for overall differences between the 3 dose levels and PCV13. All treatment groups in Stage 1 will be compared, followed by paired comparisons between each of the ASP3772 dose levels and PCV13 using a Wilcoxon Test. The same set of comparisons will be made for subjects in Stage 2, Group 2.

Stage 2; Group 3:

For the 11 serotypes contained in PPSV23 and not in PCV13, immunological response will be evaluated by the following endpoints at 30 days after administration of PPSV23:

- The GMFR, GSD and 95% CI in anticapsular polysaccharide IgG and OPA titer
- The proportion of subjects with a ≥ 4-fold increase in anticapsular polysaccharide IgG and OPA relative to baseline
- The GMT, GSD and 95% CI for the OPA titers
- The GMC, GSD and 95% CI for serotype-specific IgG levels.

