7 STATISTICAL METHODOLOGY

7.1 General Considerations

For continuous variables, descriptive statistics will include the number of subjects (n), mean, standard deviation, median, minimum, maximum, when applicable, or the geometric mean (GM) and geometric standard deviation (GSD). The geometric mean ratio (GMR) and 95% confidence interval (CI) will be used to compare the response following each dose of ASP3772 (1, 2, or 5 µg) to PCV13 within each stage. Calculations for the GM, the GMR and the geometric mean fold rise (GMFR) with the associated GSD and 95% CI can be found in Section 10.1, Appendix A: **Instructions to calculate the Summary statistics for the secondary endpoints**. Frequencies and percentages will be displayed for categorical data by treatment group (ASP3772 (1 µg, 2 µg, 5 µg) or PCV13) and stage. Percentages by category will be based on the number of subjects without missing data. Subjects with missing data will be treated as a separate category and not included in the denominator, unless specific methods for imputation are stated.

Summaries based on FAS and PPS (if needed) (e.g. disposition, baseline and efficacy data) will be presented by treatment group (ASP3772 (1 µg, 2 µg, 5 µg) or PCV13) and stage. All subjects treated with PCV13 will be combined according to their age group (Stage 1: Adults,

Stage 2: Elderly 65-85, 65-74 and 75-85). Data for all PPSV23 enrolled subjects will be summarized separately.

For serotypes common to PCV13 and ASP3772, the following treatment group comparisons for immunogenicity are of interest to determine the magnitude of the response following ASP3772 relative to PCV13 for each serotype within adults 18-64, within elderly 65-85 and within elderly subgroups 65-74 and 75-85.

- ASP3772 1 μ g vs PCV13
- ASP3772 2 μ g vs PCV13
- ASP3772 5 μ g vs PCV13

For all serotypes unique to ASP3772, the comparison will be post-dose relative to pre-dose.

Safety analyses and other summaries based on the SAF will be presented by treatment group (ASP3772 (1 μ g, 2 μ g, 5 μ g) or PCV13) and stage (adults 18-64 years, elderly 65-85 years). Within the elderly cohort summaries will also be provided where indicated for those 65-74 and those 75-85. All adult PCV13 subjects will be combined into a single group and all elderly PCV13 subjects will be combined into a single group consistent with the age group being analyzed. Summaries for all PPSV23 enrolled subjects will be provided separately.

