7.4 Analysis of Immunogenicity

7.4.1 Analysis of Immunogenicity Endpoints

Assessment of immunological response following ASP3772 administration relative to PCV13 is a secondary objective for this study.

Stage 1, Group 1 and Stage 2, Group 2:

The objective in Stage 1, Group 1 and Stage 2, Group 2 is to determine if ASP3772 stimulates an immunogenic response to the 13 pneumococcal serotypes that are also contained in PCV13 and to determine if ASP3772 stimulates an immunogenic response to an additional 11 serotypes contained in ASP3772. The following summaries will be given by treatment group (ASP3772: 1, 2, 5 μ g vs. PCV13) and stage for all serotypes.

OPA Titer

- GMT, GSD and 95% CI
- The ratio of the OPA GMT (each ASP3772 dose level/PCV13), the GSD and 95% CI for the ratio
- The GMFR relative to baseline, GSD and 95% CI
- The proportion of subjects with a $>$ 4-fold increase in OPA titer¹

IgG Concentration

- The GMC, GSD and 95% CI
- The ratio of the IgG GMC (each ASP3772 dose level/PCV13), the GSD and 95% CI
- The GMFR relative to baseline, GSD and 95% CI
- The proportion of subjects with a \geq 4-fold increase in anticapsular PS IgG

Values below the LLOQ will be set to $\frac{1}{2}$ LLOQ for calculation of geometric means and set to LLOQ for calculation of fold changes.

Summaries for Stage 2 subjects will be given for 65-85, 65-74 and 75-85-year olds.

An analysis of covariance (ANCOVA) model with age (65 to 74 years, 75 to 85 years) as the covariate and treatment (ASP3772 1, 2, 5 μ g) as the factor of interest will be conducted on the natural logarithm (log) of pneumococcal OPA titers and on the natural log of the IgG concentrations for each serotype to examine dose response. Provided the treatment effect is

significant, paired comparisons between the 5 μ g vs 1 μ g, followed by 5 μ g vs 2 μ g, followed by 2 μ g vs 1 μ g will be conducted. There are no adjustments to control for the Family-Wise Error Rate (FWER) for 3 comparisons for each of the 24 serotypes. A Cochran-Armitage trend test will be used to test for trend.

CCI

Stage 2; Group 3:

The objective for Stage 2, Group 3 is to obtain estimates of the immune response following PPSV23 for the 11 serotypes contained in PPSV23 and not in PCV13. Immunological response 30 days after administration of PPSV23 will be summarized as follows:

- The GMT, GSD and 95% CI for the OPA titers
- The GMC, GSD and 95% CI for serotype-specific IgG levels.

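### SAP Appendix A builds the 95% CI for the ASP3772/PCV13 geometric mean ratio from the ratio itself, not its log, so the interval contradicts its own estimate and t-test

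*SAP*

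**What the plan says.** SAP 7.1 makes the GMR with its 95% CI the way each ASP3772 dose is compared with PCV13 within each stage, and says the calculations "with the associated GSD and 95% CI can be found in Section 10.1" (Appendix A). SAP 7.4.1 then lists "The ratio of the OPA GMT (each ASP3772 dose level/PCV13), the GSD and 95% CI for the ratio", with a matching item for IgG, for all serotypes.

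Appendix A defines the GMR as the ASP3772 geometric mean over the PCV13 geometric mean. It tests GMR = 1 by a two-sample t-test on the logged values. For the interval it says "Obtain the standard error of the difference for the log transformed values" and gives the lower limit as e raised to "GMR - (TINV(0.975, n(1)+n(2)-2)) * SE_{DIFF"; the upper limit has a plus sign.

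For the between-group comparison of fold rise (GMFR), Appendix A fits log post-vaccination values on group, log baseline and their interaction. It reports 2 to the power of a coefficient that "is the estimate of the treatment group effect obtained from the ANCOVA", and adds: "If group*x is significant then there is heteroscedasticity".

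Its last item is headed "Proportion of subjects with a > 4-fold increase in OPA titer". Protocol 7.4 has "The proportion of subjects with a ≥ 4-fold increase in anticapsular polysaccharide IgG", and that bullet goes on to cover OPA.

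**The concern.** A log-scale standard error belongs with a log-scale estimate. Appendix A puts the ratio where its log should be, and nothing in the text redefines GMR as a log. The point estimate and the t-test in the same appendix are correct, so a program that follows the text would print an estimate, a p-value and an interval that disagree in one row.

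This is the only written formula for the main immunogenicity comparison. SAP Section 4 says the phase 3 dose and sample size will rest on Stage 2 responses, so an interval that can reverse the direction of an effect matters even for a secondary endpoint.

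Three smaller points arise in the same appendix:

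- The base of the logs in the GMFR comparison is not stated, yet the back-transform is a power of 2.
- The coefficient used there is not a contrast at a typical baseline.
- The OPA four-fold response is defined in two ways.

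**Working it through.** **Inputs.** Stage 2 has 99 subjects per ASP3772 dose and 3 × 33 = 99 pooled PCV13; Stage 1 has 30 and 3 × 10 = 30 (SAP 3.2). The SD of ln titre is not in the documents; I assume 0.8, 1.2 and 2.0.

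**The plan's own figure.** The one worked number, t(0.975, 19) = 2.093, reproduces. The per-arm limits, GM divided or multiplied by GSD^(t/√n), equal exp(mean log ± t × s/√n) and are correct.

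**GMR interval.** SE = SD × √(2/n).

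- At n = 99, t(0.975, 196) = 1.9721, so t × SE = 0.224 / 0.336 / 0.561.
- At n = 30, t(0.975, 58) = 2.0017, so t × SE = 0.413 / 0.620 / 1.034.

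The correct limits are exp(ln GMR ± t × SE); those written are exp(GMR ± t × SE). At 99 v 99:

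| SD | GMR | Correct 95% CI | As written |
|---|---|---|---|
| 0.8 | 1.0 | 0.80–1.25 | 2.17–3.40 |
| 1.2 | 1.0 | 0.71–1.40 | 1.94–3.81 |
| 2.0 | 1.0 | 0.57–1.75 | 1.55–4.76 |
| 0.8 | 0.5 | 0.40–0.63 | 1.32–2.06 |
| 1.2 | 0.5 | 0.36–0.70 | 1.18–2.31 |
| 2.0 | 0.5 | 0.29–0.88 | 0.94–2.89 |

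The written interval lies wholly above 1 whenever GMR > t × SE, that is for any GMR above 0.22 / 0.34 / 0.56.

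It contains its own estimate only if GMR − ln GMR ≤ t × SE. The left side is never below 1, so the SD must reach 1/(t√(2/n)) = 3.57 at 99 v 99 or 1.93 at 30 v 30. Stage 1 with SD 2.0 and GMR 1 is such a case (0.97–7.64).

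In 20,000 simulated Stage 2 trials at true GMR 1, with SD 1.0 / 1.5 / 2.0, the t-test rejected in about 5%. The written interval excluded 1 in 100 / 100 / 98%, and the corrected interval agreed with the t-test. In Stage 1 the written interval excluded 1 in 74% at SD 1.5 and 48% at SD 2.0.

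The text as read from the PDF also shows a divisor of n1+n2−2 in the CI exponent and a divisor of 2 in the alternative GMR formula. Either may come from the reading of the PDF, and the fault does not depend on them. If the df divisor is real, GMR 1.0 at SD 1.2 gives exp(0.6636/196) to exp(1.3364/196), or 1.003 to 1.007.

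**GMFR log base.** Natural log is the only base the SAP names. If it applies here and slopes are parallel, 2^(ln r) turns true ratios of 0.5 / 1.5 / 2 / 4 into 0.62 / 1.32 / 1.62 / 2.61. For a true ratio of 2 with SE 0.11, the interval 1.61–2.48 prints as 1.39–1.88; with SE 0.28, 1.15–3.47 prints as 1.10–2.37.

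**GMFR contrast.** With a group-by-baseline term and uncentred baseline, the group coefficient is the contrast at log baseline 0. Assume mean ln baseline m of 2 to 4, SD s of 0.8 to 1.5 and constant residual variance.

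- The SE at 0 is √(1 + m²/s²) times that at the mean: 1.67 (m = 2, s = 1.5) to 5.10 (m = 4, s = 0.8).
- A slope difference d shifts the ratio by exp(d × m): 1.11 (d = 0.05, m = 2) to 2.23 (d = 0.2, m = 4), in either direction.

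**Four-fold response.** SAP 7.4.1 for Groups 1 and 2, and Appendix A, require more than four-fold for OPA. Protocol 7.4 and the Group 3 item in SAP 7.4.1 use at least four-fold. If titres come in two-fold steps (assumption), P(1.5 < log2 fold rise < 2.5) is 8% to 34% for a mean log2 rise of 0 to 3 and SD (ln scale) of 0.8 to 2.0. If titres are interpolated, almost no one is affected.

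**The case against.** The strongest reply is that the intent is clear: natural logs, a t-test on logs, the SE of the log difference, then exponentiation. If the PDF text has spurious divisors, an ln could also have been lost. A programmer would probably notice Stage 2 limits that exclude their own estimate, and SAP Section 1 provides for a review of data and tables before hard lock. No success margin or power calculation rests on this interval.

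This lowers the chance that wrong limits are reported, but it does not correct the formula. The same symbol stands in both limits, after being defined as a ratio. A programmer who repairs it silently departs from the written SAP.

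More of the reply stands on the side points:

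- Powers of 2 are right if that step uses log2. The base is unstated rather than wrong.
- The between-group fold-rise ratio is specified only in Appendix A and is not among the items in SAP 7.4.1.
- Appendix A mentions the ESTIMATE option, which could carry an adjusted contrast, but gives no coefficients.
- The SE multiples above assume constant variance, whereas the SAP lets variance depend on baseline.
- No analysis step depends on the misworded sentence about heteroscedasticity.
- The strict inequality for OPA may be a PDF reading fault.
- The PROC FREQ code is illustrative and was not run.

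**Conclusion.** The concern holds. The GMR interval is wrong as written, and this follows from the appendix's own definitions without any assumption. Only its size depends on the assumed SD of ln titre (0.8 to 2.0). Within that range, every Stage 2 interval excludes its own estimate. A dose with half the PCV13 titre gets an interval wholly above 1 at SD 0.8 and 1.2.

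This must be corrected before the ratios are programmed. The per-arm GMT and GMC intervals, the dose-response ANCOVA and the primary safety analyses are not affected.

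The GMFR log base and contrast are clarifications held with medium confidence. A significant interaction there shows unequal slopes, not unequal variances. The mismatch in the four-fold definition is minor, and the point about the code is low confidence.

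**What to change.** 1. State GMR = exp(mean1 − mean0) with limits exp[(mean1 − mean0) ± t(0.975, n1+n2−2) × SE_diff]. Check the source page for the divisors 2 and n1+n2−2, and delete them if present.
2. In the GMFR comparison, back-transform the estimate and limits with exp, or state log2 throughout that step.
3. Centre log baseline at its overall mean, or write out the ESTIMATE contrast at that mean. Describe the interaction as a check of parallel slopes.
4. Use one definition of OPA four-fold response in both documents. In the PROC FREQ example, name the responder level and drop ordering by frequency.

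The cost is one SAP appendix, one bullet in SAP 7.4.1 and the analysis programs. No new data are needed.
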